5.3 VITAL SIGNS

5.3.1 Available data

The following vital signs parameters are collected: systolic (SBP) and diastolic blood pressure (DBP) in semi-supine position, pulse rate, body temperature and weight (only fixed on few visits, at other visits only in case of obvious weight change).

5.3.2 Derivation rules

Abnormalities are defined in below table.

	Pulse rate (bpm)	SBP (mmHg)	DBP (mmHg)	Temperature (°C)
Low	<40	<90	<45	<35.8
Normal	40-100	90-150	45-90	35.8-37.5
High	>100	>150	>90	>37.5

Note: For the worst-case analysis visits, as defined in section 2.2.5, an additional category low + high is defined in case there are both low and high post-baseline values.

5.3.3 Presentation of results

Vital signs parameters supine SBP, DBP and pulse rate will be summarized by means of descriptive statistics at each analysis visit by cycle and over time. Actual values and changes from baseline will be shown in the same table.

Abnormalities will be presented as cross-tabulations of the abnormality at each post-baseline analysis visit versus the baseline abnormality and as cross-tabulations of the worst-case abnormality versus the baseline abnormality. Numbers of participants with

Statistical Analysis Plan

ARGX-113-2002

Final Analysis

Final 5.0 of 31Jan2025

treatment-emergent abnormalities will also be shown. The cross-tabulation will be repeated by average treatment duration per year.

All vital signs data will be listed, but only for participants with any post-baseline abnormality.

5.4 ELECTROCARDIOGRAMS

5.4.1 Available data

The following electrocardiogram (ECG) parameters will be collected: heart rate (HR), QRS interval, PR interval, QT interval, QTcF and QTcB.

5.4.2 Derivation rules

Abnormalities for HR, QRS and PR interval are defined in below table.

	HR (bpm)	PR (ms)	QRS (ms)
Low	<40	<120	-
Normal	40-100	120-220	0-120
High	>100	>220	>120

Note: For the worst-case analysis visit, as defined in section 2.2.5, an additional category low + high is defined in case there are both low and high post-baseline values.

For QTc interval (ms), the following categories are defined:

- Actual values:
 - ≤ 450 (normal)
 - $]450; 480]$
 - $]480; 500]$
 - > 500
- Changes:
 - ≤ 30 (normal)
 - $]30; 60]$
 - > 60

Note: The worst-case, as defined in section 2.2.5, is the highest post-baseline value and associated change.

5.4.3 Presentation of results

Uncorrected QT interval and RR will only be listed.

Continuous ECG parameters will be summarized by means of descriptive statistics at each analysis visit by cycle and over time. Actual values and changes from baseline will be shown in the same table.

Abnormalities of the actual values will be presented as cross-tabulations of the abnormality at each post-baseline analysis visit, and at the worst-case analysis visit

	Statistical Analysis Plan	
ARGX-113-2002	Final Analysis	Final 5.0 of 31Jan2025

versus the baseline abnormality. Numbers and cumulative numbers over decreasing abnormalities (QTc only) of participants with treatment-emergent abnormalities will also be shown. The denominator for the percentage is the total number of participants having data for the parameter per treatment and per analysis visit in the safety analysis set.

Abnormalities of the QTc changes will be presented as tabulations of the change abnormality at each post-baseline analysis visit and at the worst-case analysis visit. Cumulative numbers over decreasing change abnormalities of participants will also be shown. The denominator for the percentage is the total number of participants having data for the parameter per treatment and per analysis visit in the safety analysis set.

The cross-tabulation and the tabulation of QTc change will be repeated by average treatment duration per year.

All ECG data will be listed, but only for participants with any post-baseline abnormality.

5.5 SUICIDALITY ASSESSMENT

5.5.1 *Available data*

This so-called suicidality assessment will be conducted by specifically asking the following question, derived from the PHQ-9 questionnaire: "Over the last 2 weeks, how often have you been bothered by thoughts that you would be better off dead, or of hurting yourself in some way?" Possible outcomes are: Not at all (0), Several days (1), More than half the days (2), Nearly every day (3).

5.5.2 *Presentation of results*

Suicidality assessment results will be presented using a frequency tabulation by analysis visit within cycle and worst over time across all cycles. The denominator for the percentage is the total number of participants per treatment and analysis visit in the safety analysis set

All suicidality assessment data will be listed, but only for participants with any post-baseline category ≥ 1 .

5.6 PHYSICAL EXAMINATIONS

Abnormal physical examination findings will be listed.

	Statistical Analysis Plan	
ARGX-113-2002	Final Analysis	Final 5.0 of 31Jan2025

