3. OBJECTIVES AND ENDPOINTS

Table 4: Study ARGX-113-2002 Objectives and Endpoints

Objectives	Endpoints
Primary	

To evaluate the long-term safety and tolerability of efgartigimod PH20 SC in participants with gMG	
Incidence and severity of AEs, incidence of SAEs, and AEs of special interest (AESIs), and changes in laboratory test results, physical examination results, vital signs, and electrocardiogram results
Secondary	

To evaluate the impact of efgartigimod PH20 SC on disease severity	
Myasthenia Gravis Activities of Daily Living (MG-ADL) total score changes from baseline and cycle baseline over time by cycle

To evaluate the effect of efgartigimod PH20 SC on PD	
Percentage reduction in levels of total immunoglobulin G (IgG) from baseline and cycle baseline over time by cyclePercentage reduction of anti-acetylcholine receptor antibodies (AChR-Ab) from baseline and cycle baseline over time by cycle in AChR-Ab seropositive participants

To evaluate the PK of efgartigimod PH20 SC	
Efgartigimod serum concentrations

To evaluate the immunogenicity of efgartigimod PH20 SC	
Incidence and prevalence of anti-drug antibodies (ADAs) to efgartigimod over timeIncidence and prevalence of neutralizing antibodies (NAb) against efgartigimod over timeIncidence and prevalence of ADAs to rHuPH20 over timeIncidence and prevalence of NAb against rHuPH20 over time

To evaluate the impact of efgartigimod PH20 SC on the QoL of the participants	
Changes in total Myasthenia Gravis Quality of Life Questionnaire (15-item scale revised) (MG-QoL15r) from baseline and cycle baseline by cycleChanges in EuroQoL 5 Dimensions 5-Level (EQ-5D-5L) visual analog scale (VAS) score from baseline and cycle baseline over time by cycleEQ-5D-5L responses to 5 dimensions (ie, mobility, self-care, usual activities, pain/discomfort, anxiety/depression) over time by cycle

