9.4.1. General Considerations

Since all participants will receive the same treatment in this open-label long-term safety study, analysis of all endpoints will be essentially descriptive. All endpoints will be summarized with descriptive statistics by treatment arm in study ARGX-113-2001 and overall among participants from study ARGX-113-2001 and also by AChR-Ab status and overall among all participants from both study ARGX-113-2001 and study ARGX-113-1705.

Summary statistics will be provided for the continuous endpoints (eg, MG-ADL total score, levels of total IgG and AChR-Abs, MG-QoL15r score, EQ-5D-5L VAS score, laboratory values, vital signs) over time (by cycle and over applicable study visits) in terms of absolute values, changes from study baseline and changes from cycle baseline.

Frequency tables will be generated for all categorical endpoints (ie, AEs, ADA against efgartigimod and ADA against rHuPH20, and EQ-5D-5L responses to 5 dimensions by cycle and overall).

[figure not shown]

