9.4.2. Primary Endpoint(s)

Summary statistics will be provided for the continuous endpoints and frequency tables will be generated for all categorical endpoints.

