10.2. Appendix 2: Clinical Laboratory Tests

The tests detailed in [Table 7](#) will be performed by the central laboratory.

Protocol-specific requirements for inclusion or exclusion of participants are detailed in [Section 5](#) of the protocol.

Additional tests may be performed at any time during the study as determined necessary by the investigator or required by local regulations.

Investigators must document their review of each laboratory safety report.

Table 7: Protocol-Required Safety Laboratory Tests

Laboratory Test	Parameter			
Hematology	RBC count platelet count hemoglobin hematocrit	RBC indices: MCV % reticulocytes	WBC count with differential ^a : basophils eosinophils lymphocytes monocytes neutrophils	
Clinical chemistry	BUN	potassium	AST/SGOT	albumin
	creatinine	sodium	ALT/SGPT	CRP
	glucose	calcium	ALP ^b	Bilirubin, total and direct
	HbA1c	GGT	HDL	LDL (measured)
	LDH	triglycerides	total cholesterol	creatinine clearance
Coagulation panel	aPTT	PT	INR	
Routine urinalysis	Specific gravity pH, glucose, protein, blood, ketones, bilirubin, nitrite, leukocyte esterase by dipstick Microscopic examination (if blood or protein is abnormal)			
Pregnancy testing	Urine hCG pregnancy test ^c (as needed for women of childbearing potential, defined in Section 10.5)			
Unscheduled tests	SARS-CoV-2			

ALP=alkaline phosphatase; ALT/SGPT=alanine aminotransferase; aPTT=activated partial thromboplastin time; AST/SGOT=aspartate aminotransferase; BUN=blood urea nitrogen; CRP=C-reactive protein; GGT=γ Glutamyl transferase; HbA1c=glycosylated hemoglobin; hCG=human chorionic gonadotropin; HDL=high density lipoprotein; INR=international normalized ratio; LDH=lactate dehydrogenase; LDL=low density lipoprotein; MCV=mean corpuscular volume; PT=prothrombin time; RBC=red blood cell; SGOT=serum glutamic-oxaloacetic transaminase; SGPT=serum glutamic pyruvic transaminase; WBC=white blood cell

Note: All samples for safety laboratory tests will be taken with the participant in the fasted state (8 hours).

^a These will be measured in percentage and absolute numbers.

^b Consider fractioning for elevated alkaline phosphatase levels.

^c Local urine testing will be standard for the protocol unless serum testing is required by local regulation or IRB/IEC.

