Adverse events will be allocated to these 3-monthly phases for an analysis over time in which participants are on efgartigimod treatment (either actively in one or more cycles or in follow-up).

In case of (partially) missing date/time fields, events will be allocated to the first 3-monthly phase that is possible based on the available parts of the AE start and stop date/time.

2.2.2 *Baseline and change from baseline*

Two baselines are defined:

- Baseline is the last available value prior to first administration of efgartigimod in the first cycle in 2002.
- Cycle n Baseline (CnB) is the last available value prior to first administration of efgartigimod in (amended) cycle n, with n=1, 2, 3, etc.

Note: for questionnaires, all assessments on the day of first administration of the IMP in cycle n are considered in the baseline selection, also those post-administration.

For immunogenicity, evaluable sample will be given priority when deriving the baseline or cycle 1 baseline. The cycle baseline for cycle 2 or higher will correspond to the value from the last visit in the previous cycle without any derivation.

Change can be calculated from baseline or CnB. Note: baseline coincides with C1B. Baseline will be considered for analyses that assess across all cycles and the CnB will be used for analyses restricted to a specific cycle, n, unless specified otherwise.

Change for safety parameters will be calculated from baseline only.

For efficacy and PD, a (percent) change can be calculated from baseline or CnB, according to the analysis.

Change from baseline at time point t = value at time point t – baseline value.

Percent change from baseline at time point t = (actual value at time point t - baseline value)*100/baseline value.

Change from CnB at time point t = value at time point t – CnB value.

Percent change from CnB at time point t = (actual value at time point t - CnB value)*100/CnB value.

2.2.3 *Relative day*

Relative days in the (amended) period (APADY) / in the study (ADY) will be calculated according to the following rule:

- Concerned date < reference date: APADY/ADY = concerned date – reference date
- Concerned date \geq reference date: APADY/ADY = concerned date – reference date + 1

The reference date for APADY is the date of the first administration of the study drug in the specific period. The reference date for ADY is the date of the first administration of the study drug in the (amended) treatment + follow-up phase of the study.

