5.2 CLINICAL LABORATORY EVALUATION

5.2.1 Available data

Per protocol, the following laboratory parameters are expected:

- Biochemistry: blood urea nitrogen (BUN), creatinine, creatinine clearance (unadjusted), glucose (fasting for 8 hours), total calcium, glycosylated hemoglobin (HbA1c), potassium, sodium, alkaline phosphatase (ALP), lactate dehydrogenase (LDH), C-reactive protein (CRP), aspartate aminotransferase (AST), alanine aminotransferase (ALT), gamma-glutamyl transferase (GGT), total bilirubin, direct bilirubin, albumin, lipid panel (total cholesterol, high density lipoprotein (HDL), low density lipoprotein (LDL), and triglycerides), international normalized ratio (INR), prothrombin time (PT), and activated partial thromboplastin time (aPTT).
- Hematology: platelet count, red blood cell count (RBC), hemoglobin, hematocrit, RBC indices (mean corpuscular volume (MCV), % reticulocytes), white blood cell (WBC) count with WBC differential (% and absolute for neutrophils, lymphocytes, monocytes, eosinophils, basophils).
- Urinalysis:
 - Continuous: specific gravity, pH
 - Categorical: glucose, protein, blood, ketones, bilirubin, nitrite, leukocyte esterase, microscopic evaluation, highly sensitive urine human chorionic gonadotropin (hCG) pregnancy test for females of childbearing potential.
- Other: Serum and urine human chorionic gonadotrophin (β -HCG), Follicle-stimulating hormone (FSH) test, SARS-CoV-2 testing
- Specialty laboratory tests: may include but not be limited to apolipoprotein B (apoB), lipoprotein A, fibrinogen, von Willebrand factor, d-dimer.

Normal ranges are available as provided by the laboratory.

5.2.2 *Derivation rules*

The following parameters will be derived:

- Estimated glomerular filtration rate (eGFR) (Chronic Kidney Disease Epidemiology Collaboration (CKD-EPI)) (mL/min/1.73m²)
= 141 * minimum(creatinine (mg/dL)/ K; 1)^α *
maximum(creatinine (mg/dL)/K; 1)^{-1.209} * 0.993^{age (years)} *
[1.018 if female] * [1.159 if race = black]

where K = 0.7 if female and K = 0.9 if male; $α$ = -0.329 if female and $α$ = -0.411 if male

Note: in case results in mg/dL are not available, results in μ mol/L will be used after conversion in mg/dL: 1 mg/dL = 88.4 μ mol/L

- Only fasted lipid samples and glucose (missing fasting status is considered as non-fasted) will be included in tabulations

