- The following lipid ratios will be calculated based on fasted samples only (missing fasting status is considered as non-fasted) and rounded as detailed in section 2.3.3:
 - total cholesterol/HDL
 - LDL/HDL
 - HDL/LDL
- The following abnormality categories will be defined:
 - Low: value < lower limit of normal range
 - Normal: lower limit of normal range \leq value \leq upper limit of normal range
 - High: value > upper limit of normal range

Note:

- Classification will be done in standardised units, using non imputed values and limits.
- For the worst-case analysis visits, as defined in section 2.2.5, an additional category low + high is defined in case there are both low and high post-baseline values.

Toxicity grades will be based on the common toxicity criteria for adverse events (CTCAE) toxicity grading list (version 5.0). The implementation of these toxicity grades for analysis is presented in appendix 9.2. Only the parameters described in appendix 9.2 will be computed, according to the declared limits for each grade.

5.2.3 *Presentation of results*

The statistical analysis will present results in standardised units, except for corrected GFR, which will be reported in mL/min/1.73m².

Continuous laboratory parameters will be summarized by means of descriptive statistics at each analysis visit by cycle and over time. Actual values and changes from baseline will be shown in the same table. Categorical urinalysis results will be listed only.

Statistical Analysis Plan

ARGX-113-2002

Final Analysis

Final 5.0 of 31Jan2025

Laboratory abnormalities will be presented as cross-tabulations of the abnormality at each post-baseline analysis visit and at the worst-case analysis visit versus the baseline abnormality. Numbers of participants with treatment-emergent abnormalities (see Definition of terms) will also be shown. The denominator for the percentage is the total number of participants having data for the parameter per treatment and per analysis visit in the safety analysis set.

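### Physical examination and categorical urinalysis, both within the primary endpoint, get listings but no planned counts; safety changes from cycle baseline are also dropped, and SAP 6.1 records neither departure

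*SAP*

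**What the plan says.** Protocol section 3 defines the primary endpoint as AE, SAE and AESI measures together with "changes in laboratory test results, physical examination results, vital signs, and electrocardiogram results". SAP 1.1 repeats this. Routine urinalysis is a row in protocol Table 7, headed "Protocol-Required Safety Laboratory Tests", so it counts as a laboratory test result.

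For the primary endpoint, protocol 9.4.2 promises summary statistics for continuous endpoints and says that "frequency tables will be generated for all categorical endpoints". Protocol 9.4.1 names laboratory values and vital signs among the continuous endpoints to be shown as absolute values, "changes from study baseline and changes from cycle baseline".

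The SAP does the following:
- Section 5.6, in full: "Abnormal physical examination findings will be listed". The only output is listing 16.2.13.1.
- Section 5.2.1 classes part of the urinalysis as "Categorical: glucose, protein, blood, ketones, bilirubin, nitrite, leukocyte esterase, microscopic evaluation", and section 5.2.3 then states: "Categorical urinalysis results will be listed only".
- Section 2.2.2: "Change for safety parameters will be calculated from baseline only".
- Section 6.1, on changes from the protocol before database lock, reads NAP. Protocol section 9 requires minor changes to the statistical methods to be documented in the SAP as changes from the protocol.

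**The concern.** No hypothesis is tested in this study, so the descriptive tables are the whole primary analysis. A component without a table has no planned summary: no number of participants affected, no denominator and no comparison with baseline. Physical examination is named in the endpoint. Dipstick nitrite and leukocyte esterase bear on infection, which is the AESI of this study. By contrast, suicidality, which the primary endpoint does not name, has a frequency table (14.3.5.1).

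The baseline question is separate. In a by-cycle table, a change from study baseline in a later cycle combines drift since study entry with the effect of the latest course. The protocol promised both scales for laboratory values and vital signs, and the SAP keeps one without saying so.

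**Working it through.** The protocol and SAP give no figure to reproduce here. The check is a comparison of text and planned outputs.

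**1. Primary endpoint component against planned output (SAP section 8)**

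| Component | Protocol 9.4.1 / 9.4.2 | SAP summary tables |
|---|---|---|
| Continuous laboratory, including urine specific gravity and pH | Summary statistics; change from study and cycle baseline | 14.3.2.1 and 14.3.2.1.1 (study baseline only); shift tables 14.3.2.2 and, for graded parameters, 14.3.2.3 |
| Vital signs | Same | 14.3.3.1 and 14.3.3.1.1 (study baseline only); shift table 14.3.3.2 |
| ECG | Summary statistics; not among the named examples in 9.4.1 | 14.3.4.1, 14.3.4.1.1, 14.3.4.2, 14.3.4.3 |
| Categorical urinalysis | Frequency tables | None |
| Physical examination | Frequency tables | None |

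Categorical urinalysis covers glucose, protein, blood, ketones, bilirubin, nitrite and leukocyte esterase (7) plus microscopy (1), so 8 parameters. SAP appendix 9.2 has no urinalysis grades, so these cannot enter through the toxicity tables. Protocol 8.2.2 names 8 body areas or systems as the minimum physical examination.

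**2. What study-baseline-only change loses**

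Let B be the study baseline, C the cycle n baseline and W the Week 4 value in cycle n. Then

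W − B = (W − C) + (C − B).

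The SAP tabulates W − B. The protocol also promised W − C.
- In cycle 1, SAP 2.2.2 notes that the two baselines coincide, so C − B = 0 and nothing is lost.
- From cycle 2, the tables give means at cycle baseline and at Week 4. Their difference equals the mean of W − C only if the same participants contribute to both. The SD of W − C cannot be recovered, because it needs the within-participant covariance.

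**3. Where a Week 4 value is scheduled**

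- Year 1 (protocol Table 1): laboratory tests and vital signs are scheduled at TPnV1 and at IPnV1 (A+28), so W − C can be calculated in each cycle with both visits.
- Year 2 onward (protocol Table 2): they are scheduled at TPnV1, at every fifth IP visit and at ET/EoS/SFU, but not at IPnV1. The fifth IP visit falls nominally at A + 28 + 4 × 21 = A+112. A scheduled Week 4 value then arises mainly when the next treatment period starts about then. The earliest start is A + 21 + 7 = A+28, and SAP 2.2.4 allocates the last assessment before a new cycle to both cycles.

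The missing within-course change is therefore mainly a year-1 matter, from cycle 2 onward.

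**The case against.** Several points on the other side carry weight.

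- *The promise of frequency tables is not airtight.* Protocol 9.4.1 lists the categorical endpoints as AEs, ADA and EQ-5D-5L responses, in a form that reads as complete, and omits physical examination and urinalysis. Section 9.4.2 is one line, identical to 9.4.3. This weakens the promise without removing it: 9.4.2 is the rule specific to the primary endpoint and covers all categorical endpoints. The 9.4.1 list also omits ECG and vital-sign abnormality categories, which the SAP does tabulate.
- *Clinically significant findings reach the AE tables.* True, and those tables give counts and percentages. However, the route depends on the investigator's judgement. Findings associated with the underlying disease are excluded unless more severe than expected (protocol 10.4.1), which matters for the neurological examination in gMG. AE tables also do not show change from baseline.
- *The listings are informative.* A reader might infer that they cannot show which abnormalities are new. The documents do not support that. SAP 5.2.3 lists all laboratory data for participants with any post-baseline abnormality, so baseline results can be read there. SAP 5.6 does not limit physical examination findings to post-baseline visits. What is missing is a planned count with a denominator, not the underlying information.
- *The endpoint table asks for cycle baseline only in efficacy, PD and QoL.* This is correct, and SAP 2.2.2 is consistent with that table. The contradiction is with protocol 9.4.1, which names laboratory values and vital signs but not ECG.

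**Conclusion.** The point stands in a limited form. Physical examination and the 8 categorical urinalysis parameters have no summary table, although they fall within the primary endpoint and 9.4.2 calls for frequency tables. Separately, SAP 2.2.2 contradicts protocol 9.4.1 on cycle baseline for laboratory values and vital signs. SAP 6.1 records neither.

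A reader might infer that dropping cycle baseline also leaves part of the primary endpoint without a result. It does not: those parameters still have changes from study baseline, by cycle and over time, and shift tables. Only the within-course change is lost, mainly in year-1 cycles after the first.

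The consequence is incomplete primary endpoint reporting; no error rate, power or estimate is affected. The conclusion assumes that 9.4.2 governs over the shorter list in 9.4.1. If the sponsor reads 9.4.1 as complete, listing-only handling breaks no promise of frequency tables, but the two parts would still lack a planned count. It is worth correcting because the remedy is cheap.

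**What to change.** 1. Add a shift table for categorical urinalysis, baseline against each post-baseline visit and worst case, in the format of 14.3.2.2. State what counts as abnormal for a dipstick or microscopy result, since SAP 5.2.2 defines only low, normal and high against the normal range.
2. Add a table of the number and percentage of participants with a physical examination abnormality new since baseline. Present it by body system if the eCRF records it that way; the documents do not show the field structure.
3. Add change from cycle baseline to by-cycle tables 14.3.2.1 and 14.3.3.1.
4. Record any departure that is kept in SAP 6.1, with its reason.

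The primary endpoint should not be redefined to match the listings. The SAP is dated 31 Jan 2025, after the latest study end date of 31 Dec 2024.

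The cost is SAP text and a few extra standard tables, with no new assessments. The physical examination table depends on how the findings were captured.
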